To ensure fidelity to the study protocol and to avoid any perceived coercion by JJ staff, TCU Institute of Behavioral Research (TCU/IBR) RAs will oversee intervention administration, including voluntary study enrollment and withdrawal if requested. Following our NIDA-funded JJ- TRIALS study protocol, NO participant information (youth participation, youth assessment responses, choices/responses selected during the intervention, completion of sessions) will be shared with JJ staff; only aggregate information will be shared with JJ leadership.

11. Location:

All intervention and assessments sessions will take place either online using a platform such as Zoom, in-person at a Tarrant County Juvenile Services office or another public place, or via a tablet hand-off in an agreed upon public place. All TCU rules and regulations regarding COVID-19

protocols will be followed for in-person interactions including masking, hand-washing/sanitizing, social distancing when able, and sanitizing of all equipment.

12. Subject Population:

Participants will include juvenile justice-involved youth on probation within at least 1 local juvenile probation department (Tarrant County, currently). The Tarrant County Board (TCJS) has granted preliminary approval to submit appropriate requests to TJJD to move forward with planning this study.

We expect to recruit approximately 60 youth who range in age from 14 to 18 years old.

Inclusion Criteria: Youth ages 14-18 on community supervision are eligible if they have 1 or more indicator(s) of substance use, are English-speaking, and have no indication of current suicide risk or severe cognitive impairment/thought disorders. Youth's parent/legal guardian may be Spanish-speaking. Upon approval of the parental consent document, it will be translated into Spanish and submitted to the IRB for approval.

Exclusion criteria: Youth who are on TJJD (state) supervision rather than county supervision are not eligible to participate. In addition, youth who are currently suicidal, homicidal, or otherwise severely impaired (e.g., active psychotic symptoms) such as severe cognitive impairment or thought disorders are not eligible. Youth younger than 14 and youth 19 or older are likewise not eligible.

13. Recruitment Procedure:

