Prior to study start, TCU will meet virtually with TCJS leadership to finalize recruitment, compensation, study implementation, and sharing of youth records. The TCJS Director of Research (DOR) will work directly with TCU and TJJD to ensure that data sharing agreements and procedures for linking study data to youth records are appropriate and secure. For study management purposes providing incentives to families, the DOR will know which youth are participating in the study but will keep this information confidential; supervising officers will not have access to this information. Information shared between the DOR and research team will be retained in and shared via a Box (account owned by TCU) folder with access restricted to the DOR and research team. Prior to participant recruitment, RAs will be trained on the general study protocol (e.g., recruitment, eligibility, consenting), curriculum content (e.g., rationale, content, exercises), delivery strategies, tablet operation, web access (e.g., troubleshooting, technical problem resolution), and how to address sensitive issues. RAs will be trained on identifying symptoms of trauma, handling information disclosed by youth, and will follow specific procedures required by the JJ department for reporting abuse or trauma to health personnel.

We will work with departmental staff to develop recruitment and administration procedures, including identifying the best group(s) from which to recruit participants and troubleshooting options for youth with challenges such as lack of access to Wi-Fi.

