To request corroborating data from the local JJ department as well as the Texas Department of Juvenile Justice (TJJD), the research team will request that the TCJS research director provide the TJJD-based identification number (PID) for consenting participants as well as demographic, substance screening and assessment, and relevant service attendance information. These data will be shared via a spreadsheet available to the director of research and the research team via Box.com – a secure file-sharing platform. The research team will provide the PID numbers along with headquarters county ID to the TJJD data team via spreadsheet in a Box folder in return for state-level data specific to the youth's substance use screening and assessments as well as offense, background, and service-seeking data. The TJJD research proposal submitted in September 2020 can be found in Appendix 9. be found in Appendix 9.

Intervention

The youth will receive 4 sessions of the interactive, cloud-based intervention administered via a tablet we give them. Each session of the intervention will focus on one of topics associated with drug use and risky sex practices. The final session will include an integrated module ensuring that youth process through a scenario that examines how drug use and risky sex behaviors are related. The youth will complete the final WORK-IT scenario within the app with processing questions (see Appendix 5.7) to work through this integrated scenario and also a quiz-like activity on Kahoot to learn more about local resources for substance use and sexual health.

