The proposed studies will follow established procedures based on our previous NIDA studies outlining Common Adverse Events (AEs) and Serious Adverse Events (SAEs) for substance abuse research. Adverse events are defined as any event or outcome that has resulted in harm to the participant, has affected the participant detrimentally, has worsened as a result of participation in the study, or has resulted in increased risk to the participant or others whether or not the risk actually results in harm.

SUHRI DATA AND SAFETY MONITORING PLAN

Our Data and Safety Monitoring Plan (DSMP) will be consistent with plans and procedures we have used in our other federally-funded research projects. These include installation of an 800 (toll free) number in the US for research sites to use for reporting adverse events (AEs) to the PI, Co-Is, and research team. The PI will serve as liaison with our university IRB and will monitor and report problems and AEs as directed. Specific plans and reporting formats will be developed and reviewed and approved by the IRB prior to the onset of any research involving the proposed pilot studies. Reporting forms will be developed and participating staff will be trained to identify and report problems and AEs. The agenda for the weekly data management team meetings also will include problem and adverse events reports, and all reports will be immediately forwarded to the PI. The PI will assume overall responsibility for assuring the safety of study participants and will assure that the TCU IRB is informed of all safety issues.

Definitions of Adverse and Serious Adverse Events

The proposed studies will follow established procedures based on our previous NIDA studies outlining Common Adverse Events (AEs) and Serious Adverse Events (SAEs) for substance abuse research. Adverse events are defined as any event or outcome that has resulted in harm to the participant, has affected the participant detrimentally, has worsened as a result of participation in the study, or has resulted in increased risk to the participant or others whether or not the risk actually results in harm.

Specific Adverse Events (as observed or reported by participants or staff) include:

Violation of confidentiality (e.g., release of participant data to a non-authorized 3rd party)

Institutionalization in residential treatment or substance use rehabilitation

Probation revocation, re-arrest, reincarceration (e.g., jail, prison, juvenile detention)

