Specific Serious Adverse Events (as reported by the partner JJ agency or youth participants) include:

Drug overdose

Death

Serious injury

Life-threatening experience

Suicide attempt

Hospitalization

Impairment due to a persistent or significant disability or capacity

Unexpected events are defined as any event or outcome that was not described as a risk of participation in the research or, even though described as a risk, which has occurred with unexpected severity or frequency. These SAEs will be monitored in interim analyses and will be systematically assessed as part of the post-intervention assessment. Although the enrolled participants are not considered to be at elevated risk for suicide (due to exclusion criteria), our collaborating JJ agency screens, identifies, and monitors mental health and suicide risk on an on-going basis and adheres to all local, state and federal policies regarding required reporting and intervention procedures. Specifically, all departments within the state of Texas are required to administer the Massachusetts Youth Screening Instrument Version 2 (MAYSI-2) within 2 weeks of referral to the department. Individuals with a “caution” score are identified and immediately referred to a Psychiatrist for a full evaluation. If a child is in a detention center, they are placed under “constant watch” for observation. If not in a detention center (i.e., living at home in the community), they are triaged into a crisis intervention program operated by clinicians and supervised by a Psychiatrist. This information (suicide risk, referral to psychiatrist, program participation) is logged in the electronic record system. The same procedure is employed if a suicide risk is identified at any point during involvement with JJ.

Within 24 hours prior to the first session, the TCU research assistant (RA) will confirm with the TCJS Director of Research (DOR) that the youth has met eligibility requirements (one or more indicator of substance use; on community supervision; no indication of suicide risk or thought disorder). Biweekly, RAs will provide a list of active participants to the DOR, who will identify any youth with a newly identified risk for suicide or thought disorder. Study staff also will monitor and report disclosures of suicidal ideation during study meetings as required by law and in accordance with TCJS departmental procedures.

Plan for Monitoring Adverse Consequences

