Training of staff will include information on the definitions of SAEs and AEs and reporting procedures. SAEs will be identified by a proactive system of “incident” reports filed in relation to providing interventions or participating in the research procedures. These events will be reviewed by the PI and graded for their severity and attribution to the intervention, and ALL events will be reported in writing to the local IRB within 3 business days. Also, in accordance with local reporting requirements, all AEs occurring during the course of the study will be collected, documented, and reported by the investigators to the IRB at the time of their annual continuing reviews. The PI will prepare a summary report of all Adverse Events to be submitted to the IRB. The analysis of all adverse events accumulated-to-date will include a listing of all AEs.

Incident Reporting and Procedures

Any SAE, whether or not related to study intervention, will be reported to the PI within 24 hours of detection. Within 3 business days, the PI will submit a completed SAE report to the IRB. Written reports of adverse experiences will follow statutory regulations.

In the event that a subject either withdraws from the study or the investigators decide to discontinue a subject due to an SAE, the subject will be monitored by PI via ongoing status assessment until (1) a resolution is reached (e.g., the problem requiring hospitalization has resolved or stabilized with no further changes expected); (2) the SAE is determined to be clearly unrelated to the study intervention; or (3) the SAE results in death. Outcome of SAEs will be reported to the IRB in quarterly reports. A summary of the SAEs that occurred during the previous year will be included in the annual progress report to NIDA.

The DSM report, to be submitted with the annual progress report, will include information organized into the following sections: study description, sociodemographic characteristics of the accumulated participants at baseline (pre-intervention assessment), data on the status of study participants, quality assurance issues, regulatory issues, data on AEs and SAEs, and efficacy.

Approach for Reviewing Problems

Each AE will be classified by the PIs as serious or non-serious and appropriate reporting procedures will be followed as stated above. The PIs will classify each SAE according to the following attribution of risk categories:

Definite: SAE is clearly related to the intervention

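### Listed adverse events in youth who stop attending may go uncounted: no stated step links the requested agency records to safety reporting, and the scheduled agency check covers only two risks

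*Combined protocol and SAP*

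**What the plan says.** All references are to the combined protocol and SAP.

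- **Non-serious AEs** (section 16, Definitions of Adverse and Serious Adverse Events). The list opens with "Specific Adverse Events (as observed or reported by participants or staff) include". It includes residential placement and "Probation revocation, re-arrest, reincarceration (e.g., jail, prison, juvenile detention".
- **SAEs** (same subsection). Overdose, hospitalization, suicide attempt, death and the other listed SAEs have two named sources: the partner agency and the youth. The plan adds that they "will be systematically assessed as part of the post-intervention assessment".
- **How SAEs are found** (section 16, Plan for Monitoring Adverse Consequences). They come from incident "reports filed in relation to providing interventions or participating in the research procedures". The same subsection commits the investigators to collecting and reporting every AE during the study.
- **Scheduled agency check** (section 16, Definitions). Every two weeks the research assistants send a list of active participants to the county department's Director of Research, "who will identify any youth with a newly identified risk for suicide or thought disorder".
- **Who in the agency knows** (section 13). The Director of Research knows which youth take part, but "supervising officers will not have access to this information".
- **Records requested** (section 15, Procedures). The state agency is asked for data on "substance use screening and assessments as well as offense, background, and service-seeking data", and the county department for service attendance among other items, in both cases for consenting participants. The stated purpose is corroboration.

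**The concern.** A youth who is detained, placed in residential care or hospitalized is likely to miss study contacts because of that event. If events are found mainly through study contact, the youth with events are the ones least likely to be observed. The loss is then not random, and it lowers the counts.

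Those counts go to the IRB and to NIDA, and they inform the planned larger trial. The reporting deadlines of 24 hours and 3 business days give no protection, because they start only when an event has been detected. Section 20 keeps all participants in the outcome analyses whatever their retention, but the safety plan has no matching rule.

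**Working it through.** The plan states no event rate, dropout rate or expected AE count, so there is no figure to reproduce. The check is mainly of the text.

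**Step 1. Routes side by side**

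| Information | Named source | Stated procedure | Reaches a youth who stops attending? |
|---|---|---|---|
| Revocation, re-arrest, detention, residential placement | Participants or staff | Participants' incident reports are grouped and counted (Approach for Reviewing Problems) | No stated route |
| Overdose, hospitalization, suicide attempt, death, other SAEs | Partner agency or participants | Incident reports around study contact; questions at the post-intervention assessment | Agency is named, but with no query or schedule for these events |
| New suicide risk or thought disorder | Director of Research | Biweekly list | Depends on the meaning of *active* |
| Offense, background and service data | State agency and county department | Record request for consenting participants | Yes, but no stated link to AE reporting and no extraction date |

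The last row has the coverage that the first row lacks, and the plan does not connect them.

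**Step 2. Could the agency report unprompted?** Supervising officers are not told who participates, so they cannot knowingly report a study event. The Director of Research can, but the only scheduled question to that role covers two risks.

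**Step 3. The assessment route.** The systematic questions are worded for SAEs, not for the non-serious list. They reach only youth who attend. Section 15 describes two follow-up assessments, and section 16 does not say which is meant.

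**Step 4. Illustration only.** From the document: N = 60 (section 12: "We expect to recruit approximately 60 youth who range in age from 14 to 18 years old"). Assumed: dropout d, event rate p in retained youth, rate ratio r in dropouts, and no capture at all in dropouts.

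- Missed events = N × d × p × r. Seen events = N × (1 − d) × p. Share missed = d × r / (1 − d + d × r).
- d = 20%, p = 10%, r = 1: 12 youth drop out. Missed = 12 × 0.10 = 1.2; seen = 48 × 0.10 = 4.8; total 6.0; share 20%. Chance of missing at least one = 1 − 0.90^12 = 0.72.
- Same d and p, r = 2: missed = 12 × 0.20 = 2.4; total 7.2; share 33%. Chance of missing at least one = 1 − 0.80^12 = 0.93.
- Over d = 10% to 40%: share missed is 10% to 40% with r = 1, and 18% (0.2/1.1) to 57% (0.8/1.4) with r = 2.

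**Step 5. Effect on the plan's own 5% line** (Approach for Reviewing Problems). If all 60 youth form the intervention group, 5% is 0.05 × 60 = 3 youth. Missing one gives 2/60 = 3.3%. With r = 1, a true 5% incidence would show as 2.7/60 = 4.5% at 10% dropout and 1.8/60 = 3.0% at 40%. This concerns only the incidence half of that rule; the other half is a comparison between groups.

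**The case against.** The strongest case on the other side has four parts.

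1. *The agency is a source.* This stands for SAEs: the plan names it, so a reader who infers that SAEs come only from participants, staff and incident reports goes too far. What is missing is a query or schedule for those events.
2. *Agency data are requested beyond suicide risk and thought disorder.* This also stands. The section 15 request covers offense and service data and does not depend on attendance. The documents do not say that these records will be kept out of AE counts; they state no link. The two-risk limit applies to the scheduled safety check alone.
3. *Contact need not end with a missed session.* Research assistants hold youth and caregiver contact details, staff are trained, a toll-free line is planned, and research procedures are broader than sessions. *Active* might mean anyone enrolled and not withdrawn. All of this could reduce the loss, but none of it is a stated procedure for finding events in youth who stop attending. The investigator's monitoring after withdrawal or discontinuation concerns a known SAE; it does not search for new events.
4. *Operational detail is deferred* to reporting formats and data-sharing agreements (sections 13, 16 and 19). This limits how firmly an omission can be asserted, but it does not supply the missing step.

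A reader might also infer that the county department holds overdose and hospitalization data. The documents support offense data, chiefly from the state agency, and a county record of suicide risk, psychiatric referral and program participation. They do not show that overdose or hospitalization is recorded there.

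**Conclusion.** The point holds in a limited form. As written, revocation, re-arrest, detention and residential placement are ascertained from participants or staff, although records bearing on them are already requested. For SAEs the agency is a named source without a scheduled query for the listed events. Counts therefore depend largely on attendance, and events in youth who stop attending may go uncounted despite the commitment to collect every AE.

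The direction of any loss is downward. Its size is unknown: the shares and counts in the working rest on assumed dropout and event rates and on no capture by caregivers, staff or the agency. It would be too strong to say that such events do go uncounted, or to put a number of youth on the loss.

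**What to change.** - **Coverage.** Define the biweekly list as every consented youth until the 3-month assessment date has passed, except where consent to records is withdrawn. State how that date is counted, because section 15 dates the follow-up from the last session in one place and from baseline in another.
- **Question.** Ask the Director of Research to flag any listed AE or SAE that county records show, alongside suicide risk and thought disorder. Acknowledge that overdose and hospitalization may not be in those records.
- **Records.** Count re-arrest, revocation and detention from the county and state records for all consented youth through month 3, with participant and staff report as a second source. State when the records are extracted.
- **Assessments.** Ask the AE and SAE questions at both the 1-month and 3-month assessments.
- **Reporting.** Give AE counts together with the number of youth ascertained by each source.

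The cost is somewhat more lookup time for the Director of Research, higher reported AE counts, and possibly an update to the data-sharing agreement or the IRB-approved wording. Supervising officers would still not learn who takes part, because the information flows from the agency to the study through a role that already knows.

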Research shows that technology-based interventions are associated with reductions in substance use (Champion, Newton, Barrett, & Teesson, 2013; Tait, & Christensen, 2010), and have comparable outcomes to counselor-led interventions, with the added benefits of greater cost-efficiency and treatment access (Bickle, Christensen, & Marsch, 2011; Rooke, 2010).

Technology-based interventions can ensure intervention fidelity, promote greater responsiveness to and enjoyment of program content (Carroll et al., 2008), enable customization and participant choice in activities, and facilitate diffusion and widespread adoption.

SUHRI will include four 60 – 90 minutes sessions proctored by a TCU Research Assistant (RA). Each session will entail interaction with the web-based intervention; and the last 10 minutes will involve interaction with the RA processing session content. RA prompts will include, "Do you have any questions about the material?" "Did anything about the material make you uncomfortable?" This "check in" will enable youth to talk with someone if they have questions/concerns and allow the RA to intervene with an immediate referral to an identified clinician if needed (RAs will receive training in accordance with juvenile justice departmental procedures). Each session includes an introduction to the topic, key facts/strategies for making healthy choices, scenarios and games where youth practice decision making using ACSs, and information about services available to help. Throughout all sessions, ACSs based on a MEC worksheet called WORK-IT are used to provide information, encourage introspection and problem identification, and develop/improve analytical problem-solving skills. Sessions encompass 3 core processes that are recognized components of executive function: goal setting, evaluating options, and implementing the best option. Sessions also will include additional activities to enhance decision-making skills: multiple perspective taking, rating options along several dimensions, and determining implementation intentions.

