Following assent and assessment the youth will receive a tablet to use during the study. The RA will walk through a tutorial with youth to ensure they learn how to use the tablet. The youth will then have the first intervention session with the RA. The RA will complete administrative procedures to ensure the youth is presented with the correct modules for the session, and the youth will complete the session independently with the RA available to answer questions. Once the youth completes the session, they will complete an end of session evaluation (using Qualtrics), and the RA will transition the youth out of the session and schedule the next session or the follow-up assessment (following the 4th session of the intervention).

The first intervention session will occur approximately a week after the consent/assent meeting, and each session will occur a week to several weeks apart (spanning across approximately 1 month).

Following the last session, the youth will be scheduled to complete a 1-month assessment either in-person or online with the RA. The youth will receive 2 reminder e-mails and text messages leading up to the assessment appointment. The youth will also complete a 3- month post- intervention assessment proctored virtually or in-person by the RA. The youth will also receive 3 reminder e-mails and text messages leading up to the final assessment. Reminder e-mails will come from the e-mail address [contact] with the subject line "SUHRI Reminder" directly to the youth's personal e-mail address to reduce the chance that another individual will see the e-mails. No reference to a research project will be made in the text.

Each follow-up assessment will last approximately 60 minutes, with intervention sessions lasting approximately 60 – 90 minutes each.

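### No scripted SAE question is described for the four sessions, and the one systematic SAE assessment falls at a follow-up visit the plan does not pin down

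*Combined protocol and SAP*

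**What the plan says.** **Systematic assessment.** Under Definitions of Adverse and Serious Adverse Events (Section 16), the plan has SAEs followed in interim analyses and adds that they "will be systematically assessed as part of the post-intervention assessment". It names one such assessment, in the singular.

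**Other routes for SAEs.**
- The SAE list is introduced with the words "Specific Serious Adverse Events (as reported by the partner JJ agency or youth participants) include".
- Under Plan for Monitoring Adverse Consequences: "SAEs will be identified by a proactive system of “incident” reports filed in relation to providing interventions or participating in the research procedures".
- Every two weeks the RAs send the list of active participants to the agency's Director of Research, "who will identify any youth with a newly identified risk for suicide or thought disorder".
- Study staff report suicidal ideation disclosed at study meetings. They are also trained to observe reactions to the protocol, and a weekly team meeting reviews event reports.

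**Contact at sessions.** Section 10 (the SUHRI description) gives the last ten minutes of each session to a talk with the RA. The two prompts it lists concern questions about the material and discomfort with it. Section 15 (Procedures) adds an end-of-session evaluation.

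**Schedule.** Section 15 (Procedures) says "each session will occur a week to several weeks apart (spanning across approximately 1 month". It then schedules a 1-month assessment following the last session and a 3-month assessment that it labels post-intervention. Section 15 (Assessment) instead places both follow-ups at 1 and 3 months after baseline.

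**Reporting clock.** An SAE goes to the PI within 24 hours of detection, and the PI's report reaches the IRB within 3 business days.

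**The concern.** The listed SAEs are drug overdose, death, serious injury, life-threatening experience, suicide attempt, hospitalization and lasting impairment. Most could happen at home between sessions and not be volunteered. The RA meets the youth four times, yet the text describes no question about such events at those meetings.

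The reporting times run from detection, not from occurrence, so a late question delays the whole chain without any deadline being missed. A youth who withdraws or is lost before the assessment may never be asked. Section 20 expects such losses. The SAE data sent to the IRB and NIDA could then be incomplete, with no record of how many youth were actually asked.

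**Working it through.** The plan states no detection time, so there is no figure to reproduce. The check has two parts.

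**1. Does another route ask every youth about every listed SAE?**

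| Route | Limit |
|---|---|
| Incident reports | Described as "reports filed in relation to providing interventions or participating in the research procedures", so an event at home between sessions is not clearly covered |
| Youth report | Depends on the youth volunteering it |
| Agency report | Supervising officers are not told who participates; the Director of Research is (Section 13) |
| Biweekly check | New suicide risk or thought disorder only |
| Monitoring at study meetings | Disclosed suicidal ideation only |
| Session check-in, as listed | Questions about the material and discomfort with it |
| Staff observation | Reactions to the study protocol |
| Weekly meeting, interim analyses | Can handle only events already detected |

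None of these, as described, puts the SAE list to each youth.

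**2. How long would an SAE wait if none of these routes caught it?**

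Assumptions: the SAE occurs just after session 1 (day 0); 1 month = 30 days and 3 months = 91 days; baseline is on the day of session 1 or 7 days before it. Both baseline timings are possible because assent and assessment may open the first session, while that session is also said to come about a week after the consent/assent meeting.

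Day of session 4:
- weekly sessions: 3 × 7 = 21
- four sessions spread over about a month: 30, so gaps of 30 / 3 = 10 days

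Wait until the systematic assessment:

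| Reading of the visit | Arithmetic | Days |
|---|---|---|
| 1 month after baseline | -7 + 30 to 0 + 30 | 23-30 |
| 1 month after the last session | 21 + 30 to 30 + 30 | 51-60 |
| 3 months after the last session | 21 + 91 to 30 + 91 | 112-121 |

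Wait if asked at the next session: 7-10 days.

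Reduction in the wait:
- first reading: 23 - 10 = 13 to 30 - 7 = 23 days
- second reading: 51 - 7 = 44 to 60 - 10 = 50 days
- third reading: 112 - 7 = 105 to 121 - 10 = 111 days

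On the post-baseline clock, the 1-month visit (day 23-30) may follow session 4 (day 21-30), coincide with it, or precede it.

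The choice of visit also decides what is covered. If only the 1-month visit carries the question, events between it and month 3 have no systematic question. If only the 3-month visit does, recall must span the whole period.

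**The case against.** The strongest reply is that the text supplied cannot show that SAEs go unasked at the sessions. The items of the end-of-session form (Appendix 6) and of the assessment battery are not in it. The two RA prompts are given as included, not as a complete list. Section 16 also says that specific plans and reporting formats are still to be developed and approved by the IRB. This stands: the point is that no scripted question is described, not that none exists.

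A reader might infer that SAEs go undetected while the sessions run. The documents do not support that. Incident reports, agency and youth reports, the biweekly check, monitoring of disclosed suicidal ideation, staff observation and weekly review all operate then. The duty to report covers any SAE, related or not. These routes narrow the gap but do not close it, for the reasons tabulated above.

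A reader might also infer that the question always comes after all four sessions. That fits the Procedures text but fails on the post-baseline clock.

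Longer waits are tempting too. Three-week gaps would put session 4 at 3 × 21 = 63 days and the visit at 93 or 154 days, but 63 days conflicts with the stated span of about one month. With such gaps, asking at the next session could take 21 days against 23 on the post-baseline clock, a gain of only 2.

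Finally, the plan contains no SAE count by session and no attribution rule based on timing, so no harm to such analyses can be claimed.

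**Conclusion.** The concern holds in limited form. The plan schedules systematic SAE assessment at one follow-up point and describes no scripted SAE question for the sessions. The concurrent routes rest on someone reporting or cover only part of the list. For an SAE just after session 1 that they miss, the delay is about three to four weeks on the shortest reading and about 16 to 17 weeks on the longest. These figures rest on the calendar assumptions stated, on sessions spanning 21 to 30 days, and on the youth attending the visit.

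SAE counts could be understated. The documents give no event rate or missed-event rate, so the size of any shortfall cannot be estimated, and that they would be understated is not shown. The change should be made, since it is cheap and improves ascertainment. The contradiction over the follow-up clock needs reconciling in any case.

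**What to change.** 1. In Section 16, Definitions of Adverse and Serious Adverse Events, state that the RA asks about the six self-reportable SAEs at the start of sessions 2, 3 and 4 and at both follow-up assessments. Each is a yes/no item covering the time since last contact, with a date. Death, the seventh, is ascertained through the agency.
2. In the DSM report, give the number of youth asked as the denominator for the SAE counts.
3. If the end-of-session form or the assessment battery already carries these items, say so in Section 16; a new form is then not needed for those contacts.
4. Reconcile Section 15 (Procedures), Section 15 (Assessment) and Section 16 on which visit is the post-intervention assessment, and on whether follow-up runs from baseline or from the last session.

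This changes data collection only. It uses contacts the RA already has, and costs one short form and a protocol amendment. The downside is slightly longer sessions and some extra reports of unrelated events, which the plan's five attribution categories can handle. The 7-10 day figure applies only to youth who attend the next session.
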